Clinical Comparison of Length of Cataract Procedures With Zeiss Lumera Versus Older Zeiss Microscope

NCT 03298841

Statistical Analysis Plan

Version 2 Author [name] Toyos Clinic Date: December 9, 2020

Study Protocol

Purpose and Relevant Scientific Background

To evaluate the operating times and surgical efficiencies of two different operating microscopes Leica StativS3B, Leica Microsystems, Wetzlar, Germany and OPMI Lumera T with Callisto software (Carl Zeiss Meditec, Inc., Dublin, CA) for uncomplicated cataract surgery at a single center. Both systems contain apochromatic optics, Schott-style glass and focused beams aligned with the microscope oculars. Lumera provides a xenon illumination source while Leica utilizes halogen as its illumination source. Xenon illumination sources generally provide greater brightness of illumination.

Methods

This was a retrospective review of surgical charts by two experienced high volume surgeons looking at total surgical times recorded in the chart. Traumatic and complicated cataract cases were excluded. Two focused beam microscopes were assessed.

Design: this was a single site prospective trial

1. Data Source

Data will be collected from procedures performed by two experienced cataract surgeons in a single surgery site specifically evaluating surgical times with two different microscopes in uncomplicated phacoemulsification procedures.

- 2. Analysis objectives
 - Data will be analyzed to evaluate whether one microscope may give an surgical efficiency advantage over the other. Both microscopes utilize apochromatic optics, Schott-style glass and focused beams aligned with microscope oculars. Lumera utilizes a xenon illumination source and Leica utilizes halogen as the illumination source.
- 3. Populations

Sequential patients undergoing uncomplicated phacoemulsification.

4. Endpoints

The primary endpoint will be operating time in minutes.

5. Statistical analysis plan

The data will be analyzed for mean time per procedure and standard deviations.

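### As the SAP is written, complicated cases can be excluded with the operating time, and probably the microscope, already known, which could favour one microscope

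*SAP*

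**What the plan says.** The relevant statements are all in the SAP.

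- **Methods**, on data collection: "This was a retrospective review of surgical charts by two experienced high volume surgeons looking at total surgical times recorded in the chart".
- **Methods**, the sentence directly after: "Traumatic and complicated cataract cases were excluded". It is in the passive and names no decision-maker, no order of steps and no definition of a complicated case.
- **Design line** below Methods: "Design: this was a single site prospective trial".
- **Section 1 (Data Source)**, in the future tense: "Data will be collected from procedures performed by two experienced cataract surgeons in a single surgery site". Here the two surgeons are the operators; nothing is said about who reads charts.
- **Section 3 (Populations)**: "Sequential patients undergoing uncomplicated phacoemulsification".
- **Section 4 (Endpoints)**: "The primary endpoint will be operating time in minutes".
- **Section 5 (Statistical analysis plan)**: "The data will be analyzed for mean time per procedure and standard deviations". Nothing further is planned.

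**The concern.** What the chart review looks at is, on its face, the primary endpoint. The exclusion of complicated cases belongs to the same account, and the SAP places no other step or earlier date between the two. Whether a case counts as complicated is a judgement, and a long duration can itself suggest the label. Someone who sees the time, and knows which microscope was used, may drop slow cases more readily from one group than from the other without intending to.

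The stake is the primary comparison itself. Excluded cases leave the data, so no later adjustment can bring them back. A summary by mean and standard deviation shows only the cases that remained.

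**Working it through.** **Step 1: what the text fixes and what it leaves open.**

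| Question | What the SAP says | Settled? |
|---|---|---|
| Are times read from charts after the event? | Methods: yes. Design line and section 1: prospective, future tense | No, contradictory |
| Who excludes cases? | Not stated | No |
| Is exclusion done before times are seen? | Not stated | No |
| Is the person excluding unaware of the microscope? | Not stated; visibility is likely in a surgical chart but is an inference | No |
| What is a complicated case? | Not defined; could be a pre-operative cataract type or an event during surgery | No |
| Does consecutive inclusion close the gap? | Section 3 takes only uncomplicated cases in sequence | No, the same judgement decides who is in the sequence |

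On the Methods wording, exclusion with the endpoint in view is therefore possible. It is not established.

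**Step 2: figures to reproduce.** There are none. The SAP states no sample size, alpha, power, effect size, standard deviation or number excluded. What follows is illustration under assumptions that are not in the document.

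**Step 3: a few slow cases.** Assume a typical case takes 10 minutes and a slow case 25. Both arms hold n cases, k of them slow. One arm drops its k slow cases and the other keeps them.

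Mean with slow cases kept: ((n − k) × 10 + 25k)/n = 10 + 15k/n. Mean with them dropped: 10. Shift: 15k/n minutes.

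| n per arm | k = 1 | k = 2 | k = 3 |
|---|---|---|---|
| 50 | 0.3 min | 0.6 min | 0.9 min |
| 30 | 0.5 min | 1.0 min | 1.5 min |

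Against the assumed 10-minute case this runs from 0.3/10 = 3% to 1.5/10 = 15%. If both arms drop all k, or neither drops any, the difference between arms is unaffected. Only uneven exclusion matters.

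**Step 4: the same question in SD units.** Assume normally distributed times, no true difference, and the longest share p of cases dropped in one arm only. With c = z(1 − p) and λ = φ(c)/(1 − p), the mean shifts by −λ SD and the SD is multiplied by √(1 − cλ − λ²).

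| Share dropped, one arm | Mean shift (SD) | SD ratio |
|---|---|---|
| 1% | −0.027 | 0.97 |
| 2% | −0.049 | 0.95 |
| 5% | −0.109 | 0.90 |
| 10% | −0.195 | 0.84 |

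Both statistics planned in section 5 would move, in the direction that makes the trimmed microscope look faster and more consistent.

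**The case against.** The strongest reply is that a reader might infer more than the text says: that the two surgeons reviewed their own charts and excluded cases with time and microscope in front of them. The SAP does not state this. The phrase about two high-volume surgeons may describe whose operations the charts record, which is how section 1 uses nearly the same description. The exclusion sentence names nobody. Visibility of the microscope is inferred. The SAP also says prospective and sequential, and under a prospective design the exclusion could have come before the outcome. Pairing complicated with traumatic may point to a pre-operative cataract type. All of this stands, and it is why the point is about what the wording permits.

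A second reply is that only the SAP is at hand, and screening order and masking are commonly left to a protocol. This stands in part: silence about masking alone would be no finding. But this document has its own study protocol heading, describes the review and the exclusion itself, and contradicts itself on whether the times already existed. The point concerns that stated account.

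Third, the illustrative figures depend wholly on assumed times, arm sizes and one-sided dropping. That is correct. It would be tempting to say that such shifts match any plausible microscope effect, but the SAP gives no expected effect, so that comparison cannot be made.

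**Conclusion.** The point holds in a conditional form. Methods describes a chart review directed at the primary endpoint together with an undefined, judgement-based exclusion. The conflicting design statements leave open whether cases were excluded once their times, and probably their microscope, were known. Restricting to a sequence of uncomplicated cases does not remove that judgement, and means with standard deviations would not expose uneven exclusion.

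Neither the existence nor the size of any bias can be shown from the document. The shifts of 0.3 to 1.5 minutes assume 10- and 25-minute cases, 30 or 50 cases per arm, and one to three cases dropped on one side only. The shifts of 0.027 to 0.195 SD assume normal times and one-sided trimming of the longest 1% to 10%. Confidence is medium. The change is worth making because it is cheap and less open to bias than the procedure described.

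**What to change.** 1. Reconcile the retrospective account in Methods with the prospective Design line and the future tense of section 1, and say when times were recorded relative to exclusion.
2. List every consecutive phacoemulsification in the study period from the surgical log.
3. Define traumatic and complicated, name who applies the exclusions, and apply them from the pre-operative record, with surgical time and microscope hidden as far as feasible.
4. Lock the list, and only then link surgical time and microscope.
5. Report the number excluded, with reason, by microscope.
6. Report mean and SD of operating time by microscope for all listed cases beside the restricted set, so that the effect of the exclusions can be seen.

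If the review is already complete, steps 2 to 6 can still be carried out on the existing charts. The cost is some repeat extraction, one count table and one additional set of summary statistics. Masking may remain incomplete if the people applying the exclusions were also the operators, since they may recall their own cases; the report should say so.

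### Section 5 plans only means and SDs: a microscope comparison pooled over the two surgeons would carry any difference in surgeon mix, and a surgeon term would remove it at low cost

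*SAP*

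**What the plan says.** Section 2 sets a comparative aim: the data are to show "whether one microscope may give an surgical efficiency advantage over the other". The endpoint in section 4 is continuous: "The primary endpoint will be operating time in minutes". Section 1 gives the source: "Data will be collected from procedures performed by two experienced cataract surgeons in a single surgery site". Section 3 defines the patients as "Sequential patients undergoing uncomplicated phacoemulsification". Methods describes the surgeons as "two experienced high volume surgeons looking at total surgical times recorded in the chart".

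Section 5 is a single sentence: "The data will be analyzed for mean time per procedure and standard deviations". It does not say whether the means are by microscope, by surgeon, by both or overall. It names no difference, test, interval or model.

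The SAP does not say how a case came to one microscope or the other, or whether each surgeon's cases were balanced between them. Methods calls the study retrospective and the Design line calls it prospective; neither describes allocation.

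**The concern.** The question is about microscopes, but each operating time also reflects who operated. If one surgeon did a larger share of the cases on one microscope, and the surgeons differ in speed, two pooled means cannot tell a microscope effect from a surgeon effect. The apparent advantage could be created, hidden or reversed by surgeon mix.

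If the mix is the same on both microscopes there is no bias, but the between-surgeon difference inflates the pooled SD and widens the interval. If the surgeons are equally fast, neither problem arises. The SAP has no figures that show which case applies, and section 5 does nothing to guard against the unfavourable one.

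**Working it through.** **Inputs.** From the SAP: two surgeons, two microscopes, a continuous endpoint in minutes, and means and SDs as the only planned summaries. It states no sample size, SD, alpha, effect size or surgeon-specific figure, so there is no planned figure to reproduce. Assumed:

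- d, the difference in mean time between surgeons: 1, 2 or 4 min
- dp, the difference between microscopes in one surgeon's share of cases: 0.1, 0.2 or 0.4, with shares centred on one half
- within-surgeon SD 3 min, n = 100 cases per microscope, surgeon counts fixed, surgeon and microscope effects additive

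**Bias.** The expected mean under a microscope is its own level plus p × d, where p is the slower surgeon's share. The pooled difference is therefore the true microscope difference plus dp × d. The range runs from 0.1 × 1 = 0.1 min to 0.4 × 4 = 1.6 min.

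**False rejection by a t-test on pooled means, no true microscope effect.** The true standard error is √(2 × 9/n). The test estimates it as √(2v/n), with v = 9 + d²p(1−p)n/(n−1) and p = 0.5 + dp/2. The rejection rate is P(|dp·d + Z√(18/n)| > t_crit √(2v/n)), with 2n − 2 degrees of freedom.

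Worked cell, d = 2 and dp = 0.2: v = 9 + 4 × 0.6 × 0.4 × 100/99 = 9.97. The estimated SE is √(2 × 9.97/100) = 0.447, and the rejection limit is 1.972 × 0.447 = 0.881 min. The true SE is √0.18 = 0.424 and the bias is 0.4 min. The upper tail is P(Z > (0.881 − 0.4)/0.424), about 12.9%, and the lower tail adds about 0.1%, giving 13.0%.

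| Surgeon difference | dp = 0.1 | dp = 0.2 | dp = 0.4 |
|---|---|---|---|
| 1 min | 5.2% | 7.0% | 14.8% |
| 2 min | 5.9% | 13.0% | 43.0% |
| 4 min | 7.7% | 31.8% | 92.7% |

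Simulation of the same model (20,000 runs per cell) agrees to within about 0.2 percentage points. In those runs the model with a surgeon term rejects in 4.9% to 5.1%, with bias under 0.01 min. The bottom-right cell is an extreme corner: 70/30 against 30/70 shares and a surgeon difference of 4/3 = 1.3 SD.

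**Sensitivity.**

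- SD of 2, 3 or 5 min in the middle cell: 21.7%, 13.0%, 7.9%.
- n = 50, dp = 0.1: 4.7%, 4.7%, 4.4% at 1, 2, 4 min, so no inflation. (These cells imply half-cases, 27.5 against 22.5, and are interpolations.)
- n = 50, dp = 0.4: 9.4%, 22.9%, 63.1%.
- n = 200, dp = 0.2: 9.6%, 23.1%, 62.4%.

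**Equal shares (dp = 0).** The pooled SD is inflated by √(9 + d²/4)/3 = 1.014, 1.054, 1.202 at 1, 2, 4 min, and the CI widens by the same factor. The pooled test rejects a true null in 4.6%, 3.8%, 1.8%. Its power for a true 1 min microscope difference is 64.0%, 60.9%, 49.3%, against 65.0% with surgeon in the model.

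**Cost of the surgeon term.** With equal case totals per surgeon and per microscope, the SE rises by 1/√(1 − dp²): 1.005 at 0.1, 1.021 at 0.2, 1.091 at 0.4. Beyond that it is 1/√0.64 = 1.25 at 0.6 and 1/√0.36 = 1.67 at 0.8. At dp = 1 the microscope effect cannot be estimated separately. These factors are before any gain from removing between-surgeon variance.

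**What adjustment leaves behind.** Suppose the microscopes were used in different periods and times shifted by 0.5 min between them. By the normal approximation, the surgeon-adjusted test (n = 100, SD 3 min) then still rejects a true null in 21.8% at dp = 0, falling to 19.1% at dp = 0.4.

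**The case against.** The strongest reply is that section 5 does not prescribe the analysis being criticised. It does not say the means will be pooled and it plans no test, so a table by surgeon and microscope would comply with it. That is correct, and the point is conditional for this reason. The rejection rates describe a t-test that a reader might apply, not one that the SAP plans. The bias in a pooled difference does not depend on any test.

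Second, nothing shows that the surgeons differ in speed or in microscope use. Methods calls both experienced and high volume, which may make a large gap less likely, and the assumed grid runs from no inflation to near-certain rejection. This also stands: the bias is possible, not demonstrated.

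Third, the protocol, which is not at hand, may balance microscopes within surgeon. If so, only the precision argument is left, a CI 1.4% to 20% wider over the assumed surgeon differences. The choice of estimate remains a matter for the SAP.

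Fourth, adjustment is cheap only if both surgeons used both microscopes to a reasonable extent, and the additive model assumes one microscope effect common to both surgeons. Both limits are real; a table by surgeon would let a reader see either.

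Finally, the missing contrast and interval are a more basic gap than the missing surgeon term. The same change to section 5 closes both.

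**Conclusion.** The concern holds in its conditional form. Followed as written, section 5 gives no microscope contrast or interval and leaves surgeon mix uncontrolled. If the comparison is made from pooled means, its validity depends on equal surgeon shares or equally fast surgeons, and the SAP secures neither. A bias anywhere from negligible to more than 1 min is compatible with the document, and the sizes rest wholly on the assumed times, shares, SD and counts. This is a change that should be made, not a demonstrated error in the result. Confidence is medium, because actual surgeon speeds and shares are unknown.

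**What to change.** Rewrite section 5 so that:

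- the primary estimate is the microscope difference in mean operating time from a linear model with microscope and surgeon as fixed effects, with a 95% CI;
- n, mean and SD are tabulated by microscope within each surgeon, which shows the imbalance and lets the common-effect assumption be judged;
- if each surgeon used only one microscope, the report states that the two effects cannot be separated;
- the report states that surgeon adjustment does not remove other non-randomised differences, such as calendar period, and does not make the comparison equivalent to a randomised one.

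The cost is SAP wording and one degree of freedom. If the surgeons are equally fast, the CI is about 0.5%, 2% or 9% wider at share differences of 0.1, 0.2 or 0.4, and the cost rises steeply beyond that. The operating surgeon must be known for each case; the SAP says only that surgical times are in the chart, so this should be confirmed.

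### Section 5 summarises operating time with no reference to surgeon, so a speed difference between the two surgeons could enter the microscope comparison

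*SAP*

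**What the plan says.** Section 1 (Data Source) names two operators at one site: "Data will be collected from procedures performed by two experienced cataract surgeons in a single surgery site specifically evaluating surgical times with two different microscopes". Section 2 (Analysis objectives) makes the aim comparative: "Data will be analyzed to evaluate whether one microscope may give an surgical efficiency advantage over the other". Section 3 (Populations) defines the cases in one line: "Sequential patients undergoing uncomplicated phacoemulsification". Section 4 (Endpoints) sets the outcome: "The primary endpoint will be operating time in minutes".

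Section 5 (Statistical analysis plan) is a single sentence: "The data will be analyzed for mean time per procedure and standard deviations". It mentions neither surgeon nor microscope. No other part of the SAP stratifies by surgeon, adjusts for surgeon or reports results by surgeon. The SAP also gives no operating times and no count of cases by surgeon and microscope.

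**The concern.** Operating time depends on who operates. The objective is a contrast between microscopes, and the only summary named is an average over procedures. If the two surgeons contribute in different proportions to the two microscopes and also differ in speed, the overall means differ even when neither surgeon is faster with either instrument. The same mechanism can hide or reverse a real microscope effect. It needs no drift over calendar time: two surgeons with constant but different speeds are enough.

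This bears on the primary endpoint and on the only stated objective. Surgeon is a foreseeable confounder, because Section 1 itself names two operators.

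**Working it through.** **Inputs from the SAP.** Two surgeons (Section 1), two microscopes, and a continuous outcome in minutes (Section 4). The SAP states no sample size, SD, effect size or case share, so there is no figure of its own to reproduce. All numbers below are assumptions.

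**Formula.** Let T be the true Lumera-minus-Leica effect, the same for both surgeons. Let D be surgeon A's mean time minus surgeon B's on the same microscope. Let p1 and p2 be surgeon A's share of the Lumera and Leica cases, and m surgeon B's mean time on Leica.

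- Overall Lumera mean = m + T + p1 × D
- Overall Leica mean = m + p2 × D
- Difference = T + (p1 − p2) × D

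The second term is the surgeon bias. It is zero when p1 = p2 or when D = 0.

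**Bias in minutes, (p1 − p2) × D:**

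| Gap D | imbalance 0 | 0.2 | 0.4 | 0.6 | 1.0 |
|---|---|---|---|---|---|
| 1 min | 0 | 0.2 | 0.4 | 0.6 | 1.0 |
| 2 min | 0 | 0.4 | 0.8 | 1.2 | 2.0 |
| 4 min | 0 | 0.8 | 1.6 | 2.4 | 4.0 |

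The last column is complete separation, with each surgeon on one microscope only. There the whole surgeon gap appears as a microscope difference, and no analysis can separate the two.

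The bias can also mask an effect. If T = −0.8 min (Lumera faster), D = 2 min and the imbalance is 0.4, the observed difference is −0.8 + 0.4 × 2 = 0.

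**Scale against sampling error.** Section 5 names no test, so this only shows proportion. Assume T = 0, D = 2 min, within-surgeon SD 3 min and 100 cases per microscope. For 70/30 shares:

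- Bias = 0.4 × 2 = 0.8 min.
- True standard error with shares fixed = √(2 × 9/100) = 0.424 min.
- Standard error an unadjusted comparison would use = √(2 × (9 + 0.7 × 0.3 × 4)/100) = 0.444 min, so the two-sided 5% threshold is 1.96 × 0.444 = 0.87 min.
- Chance of exceeding it = Φ((0.8 − 0.87)/0.424), about 44%.

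The same calculation gives about 4% at 50/50, 13% at 60/40 and 79% at 80/20.

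**After adjustment.** Within one surgeon, D cancels, so each surgeon's Lumera-minus-Leica difference estimates T whatever the shares. The additive linear model averages these differences with weights n1 × n2/(n1 + n2), where n1 and n2 are that surgeon's Lumera and Leica counts. A surgeon with n1 or n2 equal to zero gets weight zero.

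The price in precision, with SD 3 min and 100 cases per microscope:

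- 60/40: each weight is 60 × 40/100 = 24, and the standard error is √(9/48) = 0.433 min, about 2% above 0.424.
- 80/20: each weight is 80 × 20/100 = 16, and the standard error is √(9/32) = 0.530 min, about 25% above 0.424.

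**The case against.** The strongest reply is that Section 5 never says the surgeons are combined. It does not even say that means are given per microscope, and a table by surgeon and microscope would not contradict it. That is correct. The combined mean is the natural reading, not a stated rule. The point that stands is that Section 5 fixes a summary with no surgeon factor for a microscope comparison.

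Second, the harm needs unequal shares and unequal speeds, and the SAP shows neither. A reader might infer that use was in fact unbalanced, or that each surgeon kept to one microscope. The text does not support this: Section 1 is compatible with both surgeons using both instruments, though it does not establish that. How cases came to each microscope may be described in a protocol that is not at hand, so silence on allocation is no fault here. How surgeon is handled in the analysis does belong in the SAP.

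Third, a reader might also object that an overall SD overstates variation because it includes the gap between surgeons. That is not an error. An overall SD properly describes variation across procedures, and with equal shares it makes an unadjusted comparison slightly conservative (about 4% rather than 5% above).

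Finally, Section 5 defines no difference, interval or test, so surgeon is one element of a contrast still to be specified. That is fair, and it shows where the amendment belongs. It does not remove the need for it.

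**Conclusion.** The point holds as a gap in the stated analysis, not as evidence of bias in the data. Read naturally, Section 5 leads to a difference of overall means whose bias is the share imbalance times the surgeon gap. Under the assumed gaps of 1 to 4 minutes and imbalances of 0 to 0.6 this is 0 to 2.4 minutes per case, and zero is a possible value. The SAP allows neither the size nor the direction to be determined. Calling both surgeons experienced does not make them equally fast, and neither a single site nor the restriction to uncomplicated cases balances them across microscopes.

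Adjustment removes the surgeon term only if at least one surgeon used both microscopes. It yields a single answer only if the microscope effect is similar for both surgeons. Because the change is cheap and concerns the primary endpoint, it should be made.

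**What to change.** Amend Section 5 as follows:

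1. Tabulate the number of cases, mean and SD of operating time by surgeon and microscope (four cells).
2. Estimate the microscope difference from a linear model for time with microscope and surgeon as factors. State that this is a precision-weighted average of the within-surgeon differences and assumes a common microscope effect.
3. Show each surgeon's own Lumera-minus-Leica difference beside it, so that disagreement is visible.
4. State that a surgeon who used only one microscope contributes nothing to the comparison. If neither used both, report the times descriptively and draw no conclusion on microscope efficiency.

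The cost is SAP wording and one more variable. The SAP says that surgical times are in the chart but not that the operating surgeon is; it is assumed that the surgeon can be identified there. The drawback is lost precision when a surgeon used almost only one microscope.

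### Section 5 plans only unadjusted mean times for a comparative aim, with no stated rule for which case got which microscope, so surgeon mix or calendar period could be credited to the device

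*SAP*

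**What the plan says.** - **Aim (SAP Section 2):** "Data will be analyzed to evaluate whether one microscope may give an surgical efficiency advantage over the other". This is a comparison between devices, not a description of each one.
- **Analysis (SAP Section 5, complete):** "The data will be analyzed for mean time per procedure and standard deviations". No difference, confidence interval, test, covariate or surgeon term is named.
- **Design:** Methods states "This was a retrospective review of surgical charts". The line that follows states "Design: this was a single site prospective trial".
- **Operators (Section 1):** "procedures performed by two experienced cataract surgeons in a single surgery site".
- **Population (Section 3):** "Sequential patients undergoing uncomplicated phacoemulsification".

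The SAP states no rule for which case was done with which microscope. It does not say whether the two were used side by side or one after the other, or how each surgeon's cases divided between them.

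**The concern.** The only way from Section 5 to the question in Section 2 is to set one crude mean beside the other. That answers the question only if microscope use was unrelated to the other things that drive operating time. If the data come from past charts, the study did not assign the microscope.

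Two routes to confounding follow:

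- **Surgeon.** If the two surgeons differ in speed and used the microscopes in different proportions, part of the surgeon difference appears as a microscope difference.
- **Time.** If one microscope was used more in the earlier part of the series, any change over time in staff, technique, case mix or familiarity with a device is carried into the contrast.

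Either route could produce an apparent advantage where there is none, or hide a real one.

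**Working it through.** **Nothing to reproduce.** The SAP gives no sample size, SD, effect size or significance level. The figures below show how the bias depends on facts the SAP does not state. They do not estimate it.

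**Assumed inputs (none from the SAP):** mean 12 min, SD 4 min, no true microscope effect, a smooth linear fall in time of 10% or 20% over the whole series, and n = 50 or 100 cases per microscope. The total drift D is 0.10 × 12 = 1.2 min or 0.20 × 12 = 2.4 min.

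**Time-related bias in the crude difference**

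- Two consecutive blocks: the mean positions of the two groups are half the series apart, so bias = D/2 = 0.6 or 1.2 min.
- 80/20 overlap (each microscope has 80% of its cases in one half of the series): mean positions are 0.8 × 0.25 + 0.2 × 0.75 = 0.35 and 0.65, so bias = 0.30 × D = 0.36 or 0.72 min.
- Strict alternation: bias = D/(2n − 1). At n = 50 this is 1.2/99 = 0.012 or 2.4/99 = 0.024 min, which is negligible.

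**What that would do to a 5% two-sided test, if one were applied.** SE = 4 × √(2/n), which is 0.80 min at n = 50 and 0.566 min at n = 100. The false-positive rate is 1 − Φ(1.96 − bias/SE) + Φ(−1.96 − bias/SE).

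| Pattern of use | Drift | Bias (min) | n = 50 | n = 100 |
|---|---|---|---|---|
| Blocks | 10% | 0.6 | 12% | 19% |
| Blocks | 20% | 1.2 | 32% | 56% |
| 80/20 | 10% | 0.36 | 7% | 10% |
| 80/20 | 20% | 0.72 | 15% | 25% |
| Alternation | 10% to 20% | up to 0.024 | 5% | 5% |

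**Surgeon mix.** If one surgeon's share of cases differs by q between microscopes, and the surgeons differ by S, bias = q × S. With assumed q = 0.2 and S = 0.5 to 1.0 SD, that is 0.1 to 0.2 SD, or 0.4 to 0.8 min at SD 4. This does not depend on the order of use.

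**Precision cost of a date term.** The SE grows by √(1/(1 − r²)), where r is the correlation between microscope and position in the series. Position is uniform, with SD 1/√12 = 0.289, and the microscope indicator has SD 0.5.

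- Blocks: r = 0.5 × 0.5/0.289 = 0.866, variance × 4.0, SE × 2.
- 80/20: r = 0.3 × 0.5/0.289 = 0.52, variance × 1.37, SE × 1.17.
- Balanced use: r is near zero and so is the cost.

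**The case against.** Several points on the other side stand.

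- **Non-random assignment is an inference.** It follows from the chart-review wording, but the Design line says prospective, and a protocol that is not at hand could hold an allocation rule. The SAP does not establish that assignment was uncontrolled.
- **Successive periods of use are not documented.** A reader might infer them from the word sequential in Section 3 or from the title, "Zeiss Lumera Versus Older Zeiss Microscope". The first most naturally means consecutive patients. The second describes a device, not when it was used, and its comparator does not match the Leica named in the body. Side-by-side use fits the text equally well, and balanced use removes the time bias.
- **Practice gain has limited support.** Methods describes the surgeons as experienced and high volume. That does not exclude adapting to a particular device, but the SAP offers nothing for a 10% to 20% drift.
- **The rejection rates belong to a test the SAP does not name.** Means and SDs alone have no type I error rate. A linear date term also removes a linear drift by construction; a real trend need not be linear.

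What does not stand is that the gap can be left to the protocol. The estimate to report and the adjustments to make are SAP content, and Section 5 fixes both too thinly for the aim in Section 2. A prospective study without a stated allocation rule would have the same exposure.

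**Conclusion.** The point holds in conditional form. It is certain that the SAP sets a comparative aim, plans only crude means and SDs, describes its design in two incompatible ways, and gives no rule linking cases to microscopes. On the chart-review reading, surgeon mix can be credited to the device, and so can calendar period or case order if use was unbalanced over time.

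The size of any bias is unknown. Under the assumed drift it runs from about zero with balanced use to 0.6 to 1.2 min with block use. The SAP does not support the stronger statement that the comparison is biased by a learning curve or calendar trend, because the order of microscope use is not given. This should be corrected before the difference is interpreted as a microscope effect.

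**What to change.** 1. Reconcile the Methods and Design statements, and state how the microscope was determined for each case.
2. In Section 5, pre-specify the between-microscope difference in mean operating time with a 95% CI, from a linear model with microscope, surgeon and surgery date (or case order within surgeon). Report it beside the crude means and SDs.
3. If the two microscopes' periods of use do not overlap, keep the surgeon-adjusted difference as the main estimate, show the date-adjusted one as a sensitivity analysis, and describe the result as a before/after association. No model can separate device from period in that case without relying wholly on the assumed shape of the trend.

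**Cost:** SAP wording and one extra chart field, the date of surgery. The interval widens when use is unbalanced over time, with the SE about 17% larger at 80/20 overlap and doubled with no overlap. With balanced use the date term costs almost no precision.
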